To describe PD medication management, and the main reasons justifying their use, directly prior to LCIG initiation, at LCIG initiation and during long-term LCIG treatment

- To describe LCIG infusion settings and substantial dose adjustments and the respective reasons
- To describe the Healthcare Resource Utilization (HCRU)
- To identify the physician's and patient's/caregiver's overall preference for the pharmacological treatment approach using LCIG as monotherapy vs. LCIG plus add-on PD medication
- To identify predictors for achieving long-term monotherapy with LCIG vs. LCIG plus add-on PD medication, based on the patient's profile and the physician's profile
- To describe the latency from LCIG initiation until LCIG is given as a monotherapy and the average duration of LCIG monotherapy.
- To describe the latency from the initiation of LCIG therapy until the introduction or tapering of each PD medication, or until substantial dose adjustments of LCIG
- To evaluate the percentage of patients who are on LCIG monotherapy, PD medication management and HCRU for the participating countries who have enrolled a minimum of 20 study subjects

Study Design: This is a multi-country, retrospective and cross-sectional, post-marketing observational study (PMOS) of patients with APD treated with LCIG in a routine clinical setting. Patients who are receiving LCIG according to the approved local product label and reimbursement guidelines will be asked to participate.

This study will include a retrospective section, collecting the below specified data from patient's medical records from the time of the decision to start LCIG treatment until the present day, and a single study visit (cross-sectional) with clinical status and subjective assessments of patients at present time.

Patients, who have received LCIG for at least 12 months, and who satisfy all the inclusion criteria and exclusion criteria will be eligible to be enrolled into this PMOS. All eligible LCIG patients will be included consecutively at each participating study site.

The primary endpoint of this PMOS will be the percentages of APD patients on LCIG monotherapy right after LCIG initiation (after permanent system placement) and at 3, 6, 9, and 12, respectively.

The secondary endpoints are:

- Descriptive data from patient's PD medication:

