 - For add-on PD medication: percentage of patient on each PD medication (by drugs and class), total daily dose and levodopa equivalent Daily dose (LEDD), posology (number of times per day);
 - For LCIG infusion settings and substantial dose adjustments: total dose per day and specific for each type of dose (morning dose and continuous dose) and number of hours of infusion.
 - Tapering process: number of days required for the tapering process, total dose per day and posology for add-on PD medication prior to LCIG initiation, at LCIG initiation (titration) or during ongoing LCIG treatment
 - Main reasons for introduction or tapering of add-on PD medication or LCIG substantial dose adjustments
- Latency and duration of treatments data:
 - Number of days or months from LCIG initiation until LCIG is given as a monotherapy and the duration of LCIG monotherapy.
 - Number of days or months from LCIG initiation until the introduction or tapering of each PD medication, or until any LCIG substantial dose adjustments.

- LCIG monotherapy vs LCIG plus add-on PD medication data:
 - Healthcare Resource Utilization, as measured by Healthcare Resource Utilization Questionnaire (HCRU)
 - Patient's, caregiver's, and physician's overall preference on LCIG monotherapy vs. LCIG plus add-on PD medication, percentage of patient's and physician's preference for each of the options
 - Predictors for LCIG as monotherapy vs. LCIG plus add-on PD medication based on the patient's profile, including socio-demographics, clinical status (motor and nonmotor symptoms), Levodopa-equivalent dose (LED), PD medication and Quality of Life
 - Predictors for LCIG as monotherapy vs. LCIG plus add-on PD medications based on the physician's profile including experience as measured by, number of years on APD patient management, number of years using LCIG therapy, and number of patients on LCIG therapy

Population: Patients that may be enrolled in this study are adult patients with APD, who are under treatment with LCIG according to the local product label and specific reimbursement criteria. Decision to offer study participation has been made by their physician, based on meeting all of the inclusion criteria and none of the exclusion criteria.

A total of approximately 400 patients with APD will be included.

Patients must meet all of the following criteria:

- 1. Patients diagnosed with APD and on LCIG treatment for at least 12 months

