During an optional test phase with application of LCIG via a nasojejunal (NJ) tube, the treatment response and tolerability of LCIG may be assessed before proceeding to the surgical procedure to permanently place a tube into the small bowel. The percutaneous endoscopic gastrostomy with a jejunum tube placement (PEG-J) is a common procedure and typically does not require general anesthesia (mostly conscious sedation) [39]. Although the percutaneous endoscopic gastrostomy (PEG) procedure is relatively safe and major complications are rare, device- and procedure-related undesirable effects may occur. Drug-related undesirable effects that occur frequently with the Duodopa system include nausea and dyskinesia. Device- and procedure related undesirable effects include abdominal pain, complications of device insertion, excessive granulation tissue, incision site erythema, postoperative wound infection, post procedural discharge, procedural pain and procedural site reaction. Less common complications of the PEG procedure observed with the LCIG system include bezoar, ileus, implant site erosion/ulcer, intestinal hemorrhage, intestinal ischemia, intestinal obstruction, intestinal perforation, intussusception, pancreatitis, peritonitis, pneumoperitoneum and post-operative wound infection [40]. These complications may result in serious events which might impose a need for further surgery, or may be even fatal.

LCIG Clinical Data

LCIG efficacy and safety in patients has been corroborated in many clinical trials in patients with APD [4, 41-44]. Outcomes from a randomized, double-blind, controlled, multi-country study over 12 weeks in 71 patients comparing LCIG and oral levodopa/carbidopa as adjunct therapy to optimized oral treatment have been published [7]. In LCIG patients, a significant reduction in off-time versus baseline and versus oral levodopa/carbidopa as well as an increase in on-time without dyskinesias versus oral levodopa/carbidopa were observed.

A subsequent open-label extension study showed sustained efficacy in patients continuing LCIG therapy [45]. The LCIG-naïve patients, i.e. those previously randomized to oral levodopa/carbidopa in the double-blind phase, showed a similar efficacy with regard to off- and on-time without dyskinesias as the patients randomized to LCIG.

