A multi-national study focusing primarily on tolerability and safety enrolled 354 patients with APD who were observed over 54 weeks in an open-label design including a nasojejunal test phase [8, 46]. In this study, 76.8% of patients completed the study, while 7.6% of patients withdrew due to AEs. The efficacy findings confirmed the data of the above described double-dummy study [7] showing similar reductions in daily off-time and increases in on-time without dyskinesias over 1 year, and also showed sustained effects under stable levodopa doses.

In addition, interim data from an ongoing post-marketing observational study on the use of LCIG in routine care conditions showed sustained improvements in off-time and ontime with dyskinesias, as well as improvements in Unified Parkinson's Disease Rating Scale (UPDRS) II and III scores during on-time. According to the 12-month interim outcomes of the first 172 included patients, the mean LCIG dose remained stable and the

tolerability and safety data were consistent with the established safety profile of LCIG [10].

LCIG and add-on PD medication use

According to the label outside of the United States, LCIG should be initially used as a monotherapy [40]. In clinical practice however, a transitory titration period is usually needed during which all other oral or transdermal therapies are tapered. Many patients are expected to be treated sufficiently by LCIG daytime infusions. Some patients, however, may need additional therapy for the night time and eventually add-on combination therapy may be warranted, in order to increase bioavailability and effectiveness [47].

Data from the above mentioned clinical trials [7, 8, 46] also suggest that LCIG treatment can reduce the need for other PD medication.

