9.2.7.5 Previous PD medication and add-on PD treatment during **LCIG Treatment**

Data on previous PD medication (right before initiation of LCIG treatment) will include date of drug initiation and/discontinuation, reason for its discontinuation, drug name, total dose per day, posology, and attempts of previous device-aided therapies (e.g., CSAI, DBS).

Data on add-on PD medication upon LCIG initiation or during LCIG treatment will include date of drug initiation/discontinuation, drug name, total dose per day, posology, tapering* process (duration and posology), starting and end date of LCIG titration, reasons for add-on drug therapy (severity and frequency), timing of add-on drug (during/outside of infusion hours).

Levodopa equivalent daily dose (LEDD) table published by Tomlinson, et al will be used to calculate LEDD. [47]. Each PD medication amount should be multiplied by the appropriate value to obtain the corresponding LEDD. Adding together the corresponding LEDD for each PD medication, will be providing the total LEDD.

9.2.7.6 **Concomitant Disease and Medication**

Information on concomitant disease and medication (non-PD treatment) will be collected and reported in the eCRF, including drug name, indication, start/stop date, and dosages.

^{*}The term "tapering" is used within this study in the context of drug treatment. It refers to the process of reducing a certain drug dosage incrementally (over a few days or weeks), instead of its abrupt discontinuation. For some PD medications a tapering process is needed to avoid a withdrawal syndrome

9.2.7.7 **LCIG Treatment**

Information on LCIG treatment from initiation until the day of the visit will be documented in the eCRF, including reason(s) for initiation of LCIG treatment, date of introduction of LCIG, use of nasojejunal tube, date of PEG-J procedure, date of titration and duration of titration process, infusion settings (infusion time, morning dose, continuous infusion rate, total daily dose) and dose modification (number of dosage changes, new infusion settings or temporary interruptions in LCIG daily infusion rate and reasons for dosage adjustment).

A LCIG substantial dose adjustment is defined as any increase or decrease of the total daily LCIG dose by more than 20% of total daily dose.

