#### Clinical PD status immediately prior to / at LCIG initiation

- Duration of 'Off' state time during a 24h period (hours)
- Duration of dyskinesia during a 24h period (hours)
- Severity of dyskinesia
- Reason for LCIG start (multiple answers)
- Conduction of Nasojejunal test phase (yes, no)
  - If yes: reason (multiple answers)
  - If no: reason (multiple answers)
- Duration of titration calculated as date of titration finalization minus date of titration initiation +1
- Duration of LCIG treatment calculated as visit date minus date of LCIG initiation start +1
- Hospitalization for titration and PEG-J placement (yes, no)
- Hospitalization for PEG-J placement (yes, no)

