#### 6.4 Primary variable

There are two primary variables:

1. LCIG monotherapy 1 (yes, no) at LCIG initiation and at 3, 6, 9, and 12 months after LCIG initiation

with the following definition:

- LCIG monotherapy means that the patient is not on any add-on PD medication or PD therapy at the respective time point.
- 2. LCIG monotherapy 2 (yes, no) at LCIG initiation and at 3, 6, 9, and 12 months after LCIG initiation

with the following definition:

LCIG monotherapy means that the patient is allowed to take an add-on PD medication or PD therapy at the respective time point, however, only in the evening after the LCIG infusion is completed (i.e. reason for start of add-on PD medication: other).

Additional specifications for both variables are:

- Medications for indications secondary to PD are allowed.
- If the reason for add-on PD medication is missing the medication will be considered as taken during LCIG infusion (i.e. no monotherapy).
- LCIG initiation date is the start date of the first LCIG infusion.
- 3 months after LCIG initiation is calculated as LCIG initiation date + rounded (3 [months] x 30.4 [days]). 6, 9, and 12 months after LCIG initiation will be calculated analogously.
- For LCIG initiation date with missing day the 15th will be used.

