#### Reasons:

- For each add-on PD medication/therapy at the time points LCIG initiation and at 3, 6, 9, and 12 months after LCIG initiation and at visit::
  - Reason for start (multiple answers)
  - If not ongoing: reason for discontinuation (multiple answers)
- Reason for change on LCIG dose in general
- Reason for LCIG dose changes (multiple answers) by 5%, 10%, 15%, 20% or 25% or higher
- Reason for substantial LCIG dose changes (multiple answers) with substantial change defined as any increase or decrease of the total daily LCIG dose by more than 20%
- Latency and duration of treatments:
  - For patients with add-on PD medication or PD therapy at LCIG initiation: Time from LCIG initiation until LCIG is given as a monotherapy (separately for monotherapy 1 and monotherapy 2 definition)

[figure not shown]
Only patients with add-on PD medication or PD therapy at LCIG initiation

 For patients with add-on PD medication or PD therapy at LCIG initiation and separately for patients with and without ongoing monotherapy at visit: Duration of LCIG monotherapy (separately for monotherapy 1 and monotherapy 2 definition) Only patients with add-on PD medication or PD therapy at LCIG initiation Analysis a) Without ongoing monotherapy until visit

Analysis b) With ongoing monotherapy until visit

- For each add-on PD medication/therapy:
   Time from LCIG initiation until the respective add-on PD medication/therapy is started or changed
- Time from LCIG initiation until the first LCIG dose change by 5%, 10%, 15%, 20% or 25%
- Time from LCIG initiation until the first substantial LCIG dose change with substantial change defined as any increase or decrease of the total daily LCIG dose by more than 20% in relation to first LCIG infusion
- LCIG monotherapy (1 and 2) vs. LCIG plus add-on PD medication:
  - o HCRU:
    - Primary occupation (retired, on sick leave, unemployed, working full time, working part-time, student)
      - If retired: due to PD (yes, no)
      - If on sick leave: due to PD (yes, no)
      - If unemployed: due to PD (yes, no)
    - Permanent living in a nursing home/institution (yes, no)
    - Help in daily activities
    - Frequency of visits:
      - General practitioner

- Nurse
- Occupational/speech therapist
- Physiotherapist
- Psychologist and/or psychiatrist
- Dietician
- Discussion of LCIG monotherapy (yes, no, patient did not remember)
- Offering of LCIG monotherapy (yes, no, patient did not remember)

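### Time to first substantial LCIG dose change is measured against the first infusion, so titration steps may count as the event and the 20% threshold for later changes can be distorted

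*SAP*

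**What the plan says.** The SAP's latency bullet (6.5, latency and duration of treatments) runs from LCIG initiation to the first substantial change, defined as "any increase or decrease of the total daily LCIG dose by more than 20% in relation to first LCIG infusion". SAP 6.4 fixes the time origin at the same point: "LCIG initiation date is the start date of the first LCIG infusion".

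Two neighbouring variables in SAP 6.5 have no stated reference dose: the reasons for substantial dose changes (same 20% threshold), and the time to the first change at thresholds from 5% to 25%. Protocol 9.2.7.7 has none either; it defines a substantial adjustment as "any increase or decrease of the total daily LCIG dose by more than 20% of total daily dose".

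Several places bear on where the first infusion falls:

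- In the protocol's endpoint list (4.0 and 9.1), the tapering item separates two phases: "at LCIG initiation (titration) or during ongoing LCIG treatment".
- Protocol 7.0 says that "a transitory titration period is usually needed" in practice.
- Protocol 7.0 also allows LCIG before the permanent tube: "During an optional test phase with application of LCIG via a nasojejunal (NJ) tube".
- The primary endpoint in the abstract (4.0) is worded "right after LCIG initiation (after permanent system placement", a later point than a nasojejunal first infusion would be.

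Titration dates are available to the analysis, because SAP 6.3 uses them for another variable: "Duration of titration calculated as date of titration finalization minus date of titration initiation +1".

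**The concern.** Clock and reference dose share one point, the first infusion, which on the documents' description lies at the start of initiation and titration and may lie in the nasojejunal test phase. The stated secondary objective is to describe how long patients go before a substantial LCIG dose adjustment. If titration steps enter the record, the variable can instead return a date within titration, and because only the first event counts, nothing later in that patient's history can change it. Where titration is modest, the reference stays at a dose the patient has already left, so a nominal 20% rule becomes lopsided around the dose actually in use. Readers of the report would take the result as time to adjustment of an established dose.

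**Working it through.** **The plan's own figure.** The SAP and protocol give no number for this variable. The only computed figure is the study size: 1.96² × 0.25 / 0.05² = 384.15, rounded up to 385. It reproduces and does not bear on this point.

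**Inputs from the documents.** An event is a change of more than 20% up or down; the reference is the first infusion; only the first event counts; no rule excludes titration (SAP 6.4, 6.5). Doses and days below are illustrative.

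**The rule in symbols.** Let D0 be the total daily dose at the first infusion and r the settled dose after titration divided by D0. An event needs dose/D0 above 1.2 or below 0.8.

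- If r > 1.2 or r < 0.8, the event is dated within titration.
- If r lies between 0.8 and 1.2, a later change from the settled dose registers only above 1.2/r − 1 (rise) or 1 − 0.8/r (cut).

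| r | Rise needed | Cut needed |
|---|---|---|
| 0.90 | 33.3% | 11.1% |
| 1.00 | 20.0% | 20.0% |
| 1.10 | 9.1% | 27.3% |
| 1.15 | 4.3% | 30.4% |

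**Worked dose paths (mL/day).** The last column uses the dose at the end of titration as reference and counts later changes only.

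| Path | SAP rule | End-of-titration reference |
|---|---|---|
| 60, 70, 80 by day 7; 100 on day 300 | day 7 (80/60 = +33.3%) | day 300 (100/80 = +25%) |
| 80, 100 by day 5; then essentially stable | day 5 (100/80 = +25%) | no event |
| 80, 92 by day 7; 69 on day 300 | no event (69/80 = −13.75%) | day 300 (69/92 = −25%) |
| 80, 92 by day 7; 97 on day 300 | day 300 (97/80 = +21.25%) | no event (97/92 = +5.4%) |

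The first two paths show the event landing in titration. The last two (r = 92/80 = 1.15) show a real change missed and a small one counted.

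**How often, under assumption only.** Suppose r is lognormal with median 1.0 to 1.3 and log-SD 0.1 to 0.3. With median m and log-SD s, the share with an event in titration is Φ(ln(0.8/m)/s) + 1 − Φ(ln(1.2/m)/s). For m = 1.0, s = 0.1 this is 0.013 + 0.034 = 0.05; for m = 1.3, s = 0.1 it is 0.79. Simulation over the whole grid gives 5% to 79%. Among the remaining patients, suppose each has one later 25% change, half up and half down. A rise is missed when r ≤ 1.2/1.25 = 0.96, and a cut when r ≥ 0.8/0.75 = 1.067; between 29% and 45% of these changes are missed. The width of these ranges shows that the documents do not settle the frequency.

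**The case against.** The strongest reply is that the documents do not show an untitrated first dose in the data. Protocol 9.2.7.7 lists the titration date and duration separately from infusion settings and dose modifications, and the recording form is not available. If sites enter only a first settled setting, the titration effect shrinks. Nor does any section say how large LCIG dose steps are in titration; protocol 7.0 describes that period mainly as one in which other therapies are tapered. This stands, and it is why the point is conditional.

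A reader might also infer that the SAP contradicts the protocol, or that the reasons and latency outputs describe different events. Neither is supported. The protocol names no reference dose, so the SAP fills a gap; the reasons bullet is silent, and silence is not a different reference. What can be said is that the reference is stated once and left open elsewhere.

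The protocol measures from initiation and covers any substantial adjustment, so counting only post-titration changes narrows its endpoint. That is a fair cost, and a reason to keep a version that includes titration. A fixed reference also has merit: against the preceding dose, a stepwise rise of 100, 115, 130, 149 mL (+15%, +13%, +15%) never registers although the total is +49%.

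Other outputs limit the harm. Titration duration is reported (SAP 6.3), total daily dose is summarised at set time points through to the visit (SAP 6.5), and the difference between visit and month 12 (SAP 7.6) does not involve the first infusion. None of these gives the time to a first substantial change.

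**Conclusion.** The concern holds as a defect of definition. As written, the rule allows a titration step to be the event, and where titration stays within 20% it misplaces the threshold for later changes; at r = 1.15 the nominal ±20% becomes +4.3% and −30.4% around the settled dose. The first effect depends on titration settings being recorded; the second needs the settled dose to differ from the first recorded one.

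A reader might go further and conclude that the median latency lies inside titration, or that latency simply equals titration length. The documents do not support either: the first needs more than half of patients to be titrated by over 20%, which is not known, and the event falls within titration rather than at its end. Nor, in a patient whose titration exceeds 20%, does the fixed reference hide later changes; the clock has already stopped.

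The variable is secondary and descriptive. The primary endpoint, the regression models and the study size are untouched. It does answer a stated objective, and SAP 2.5 makes the SAP's methods binding for programming, so the wording is worth correcting. SAP 7.10 would allow a later change, but a reference chosen after seeing the data is weaker than one set beforehand.

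**What to change.** In SAP 6.5, state one reference dose for all LCIG dose-change variables, both latency and reasons: the total daily dose at the recorded date of titration finalization. Count substantial changes after that date, still reporting time from LCIG initiation as the protocol objective asks. Tabulate titration-phase changes separately; SAP 6.6 already splits adverse reactions between initiation and maintenance. The first-infusion version can stay as a supplementary summary.

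The cost is SAP wording and a small amount of programming, since titration dates and infusion settings are already collected. Patients without a recorded titration end date need a fallback named in advance, and their number should be reported. If the dose just before each change is preferred as reference, the SAP should say that stepwise drift can go uncounted. All of this concerns the analysis definition only, not how LCIG is dosed.
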